#### **H. PRIVACY:**

All information that is obtained from participants will be used for the specifically stated purposes that are described in this Project Description, and after approval by the HSS. The personal identifiers that are necessary for this research and that will be obtained are the following: Name, Medical Record Number, Age, Gender, Medical and Psychiatric History, and Laboratory Examination. The procedures for data collection and recruitment of participants, described elsewhere in the project description, are the least intrusive consistent with obtaining the information necessary to complete this project.

[name] M.D., Ph.D., [name] [name]., and [name] R.N will review medical records to extract research information. All members of the research team will review, use, and record the minimum amount of information necessary to accomplish the goals outlined in the protocol. No study related procedures will invade into participant's privacy.

All members of the research team have been trained on HIC and VHA privacy regulations and policies and training are current. The data collected as part of this study may be made available to the VA, the US FDA, and NIDA. Participants are informed of these possibilities in the consent form. Demographic and outcome data described earlier will be collected as part of this study. Personnel listed on protocol will have access to data containing PHI. As noted above, limited PHI may be disclosed to the FDA, as required.

The settings in which informed consent discussions, other participant interviews or research procedures occur will provide the same privacy protections that would exist if these discussions, interviews, or procedures were carried out for required clinical care (private rooms, drawn curtains, etc.). The information will be used for this project, or disclosed to others, only as permitted by the Privacy Act, the HIPAA Privacy Rule, and VA policy.

The hardcopy data will be stored in locked file cabinets on the campus of VA Connecticut Healthcare System. Some electronic data including demographic data, screening data, laboratory data and RN/MD progress notes about each visit, etc. will be stored on the VA CPRS system.

#### **I. SELECTION:**

Participants will be recruited through the VA methadone and buprenorphine clinics, as well as through community (i.e., APT Foundation and New Era) and Opioid Treatment Programs. After the initial phone screening, potential participants will undergo a comprehensive evaluation, which will include medical, psychiatric, and drug use histories as well as physical, psychiatric, and laboratory examinations (see K.2. "Screening").

If participants are noncompliant (i.e., repeated no-shows) participation will be terminated.

#### **J. RECRUITMENT:**

Potential participants will be identified through responses to flyers, web postings craigslist, as well as clinicaltrials.gov and BuildClinical. Furthermore, the research team will reach out to local mental health and substance use disorder treatment facilities – including local methadone and buprenorphine clinics – for patient referrals.

Participants will be asked to contact research staff through the advertisement methods listed above. If a participant responds to an advertisement, they will be contacting study staff. If a participant is referred from substance use disorder or mental health facility, research staff will require that the participant's clinician contacts the participant first and then refers the participant to the research clinic. Participants known to us from participation in other studies who agreed to be re-contacted will also be contacted.

The PI and some co-investigators may provide clinical care to some potential participants and/or may work in the clinic where some potential participants are treated.

**J.1. Build Clinical Screening:** Build Clinical is an additional service that improves the predictability of recruitment. It involves operationalizing the study's enrollment criteria in an online questionnaire, ahead of the phone screening. Build Clinical services have been successfully utilized by several investigatory at Yale and State of Connecticut Department of Mental Health and Addiction Services

**J.2. Phone Screening:** Participants who respond to the various recruitment strategies will be provided the Mental Illness Research, Education and Clinical Center (MIRECC) central recruitment telephone number to contact a member of the research team. At the first telephone contact, a brief telephone prescreening will be conducted with the verbal assent of the participant. The purpose of the prescreening is to save both potential participants and the research staff a considerable amount of time and effort. Participants find it quite burdensome to commit the time and effort for a face-to-face screening only to find out that they are ineligible for some obvious exclusion criterion e.g., age. At the very beginning of the telephone prescreening, potential participants will be first provided a summary of the studies they may be interested in. They will also be asked about allergies that may interfere with participation in the study (i.e., sesame allergies).

If a participant expresses an interest in participating in one of the studies, the participants will be told the following:

*"We would like to ask you some general information to determine whether you might qualify for the study. This information will only be used to determine your eligibility to participate in research. This information will be stored in secure research files. If you do not want any information about you stored, we will terminate this interview now. If you agree to proceed ahead with this preliminary interview and seem to be eligible to participate in this study, we may invite you for a face-to-face meeting."*

If they pass the initial brief screening for the study, they will then come into the clinic for a full screening evaluation. Upon arrival, the participants will be given the detailed consent form to read and will be asked questions to make sure that the participants understand the procedures and their rights and written informed consent will be obtained. Information collected during the phone screen will only be used if the participant continues to participate in the study.

**J.3. Face to Face Screening:** This will include written informed consent followed by screening procedures. Please see screening section under research plan for more details.

**J.4. Consent Procedures:** Potential participants will be invited to meet with the research staff, who will fully explain the risks and procedures as outlined in the consent form. After reviewing this information and answering questions, informed consent will be obtained from all participants. A copy of the consent form will be provided to all participants. After signing the consent form, participants will proceed with screening. Once all screening procedures have been collected, research staff as well as the principal investigator will review all relevant information and determine, based on the inclusion and exclusion criteria, if the participant will be enrolled in the study and continue with the remaining study procedures. Participants already on pharmacotherapy specified in the protocol will continue use of the medications while participating in the current study. Participants will not be taken off their current medications for participation in this study.

## **K. RESEARCH PLAN:**

**K.1. Study design:** This project will consist of 2 sub-studies.

**K.1.1. Pilot safety data sub-study:** The first study will be a pilot study in which 6 participants (3 receiving methadone, and 3 receiving buprenorphine) will receive ascending doses of CBD, to determine its safety and tolerability of this medication. Participants will be stratified based on whether they are receiving methadone and buprenorphine. This open-label phase will inform the conduction of the general study. Participants will be receiving either buprenorphine (up to 24 mg/day sublingual tablets) or methadone from their designated opioid treatment program and will thereby be at steady state at enrollment. Participants will receive consecutive doses of 400 mg, 800 mg, and 1200 mg, over a total of 3 test sessions, with at least 72 hours of interval between each test session, using a dose-escalation paradigm.

If we encounter no clinically significant sedation or serious adverse events during the test session, participants will be eligible to receive the next CBD dose – at least 72 hours later. Clinically significant sedation will be defined as Agitation and Calmness Evaluation Scale (ACES) scores of 7 (marked calmness) or higher at any point during the session, or no return to baseline – assessed with vital signs, Mini Mental Status Exam (MMSE), and a field test – 3 hours after the administration of buprenorphine, or 4 hours after the administration of methadone. Serious adverse events will be defined in accordance with FDA guidelines. If 2 participants experience clinically significant sedation, defined as above, or serious adverse events, study enrollment will be stopped until the Data Safety Monitoring Board (DSMB) examines the findings. Randomization to distinct doses of CBD, using the general study design described below, will not occur before the safety data is analyzed, in consultation with the DSMB.

**K.1.2 General study:** This is a double-blind, randomized, placebo-controlled, cross-over human laboratory study. Thirty-four male and female participants with OUD on MAT will be asked to arrive at approximately the same time each morning, coordinating with attendance at their opioid maintenance clinic. Participants will be stratified based on whether they are receiving methadone or buprenorphine. This will ensure that the safety and efficacy of CBD can be tested in each arm. On test days, all participants will be asked to refrain from caffeine, nicotine, and will be fasting on the test days. A study nurse will confirm with their respective program that participants did not receive either methadone or buprenorphine that morning and will call the program when testing is complete to permit dispersal of that day's methadone or buprenorphine dose. Participants will undergo a variety of cognitive and self-report measures, as well as assessments to confirm restraint from illicit drug use and lack of adverse effects of medication. Participants are asked to have blood draws during testing session, but this is optional. Participants who give permission to have this blood drawn will have an IV placed will have it placed the morning of each test session. If a subject chooses not to have an IV, only safety bloods will be drawn. Prior to their daily methadone or buprenorphine dose and thus at trough plasma levels of opioid, participants will receive CBD (400 mg, 800 mg, 1200 mg) or placebo, over a total of four sessions. Subsequently, all participants will undergo laboratory testing of measures relevant to vulnerability to relapse, including physiological, subjective, and cognitive outcomes. Participants will be observed for at

least 6 hours after the administration of CBD/placebo, and for 2 hours after the administration of buprenorphine/methadone. In case participants experience any sedation beyond these time points, observation will continue, —consistent with procedures in our research clinic (HSS #JD002). The order of study medication administration will be counterbalanced to reduce perceived bias of study participants and staff.

Justification for not requiring blood testing during test sessions: The primary aim of our study is to establish the safety and analgesic and craving suppression efficacy of cannabidiol (CBD) among persons with opioid use disorder who are receiving opioid agonist therapy. Our study was designed to look at pharmacodynamic effects of CBD in this population, rather than to investigate the relationship between pharmacokinetic and pharmacodynamic effects of CBD. Accordingly, drug levels are an exploratory outcome.

While the blood collection does not represent a “critical data point” of this study, collecting these data in a subset of participants will allow establishing the feasibility of conducting adequately powered pharmacokinetic studies — a next logical step of our research.

In conducting this work, we observed that, since a substantial proportion of our participants have a history of intravenous drug use, obtaining an intravenous line can often be challenging and may require multiple attempts that can produce participant discomfort. Therefore, by giving the participants the choice of opting out of this procedure, we will reduce participant burden without compromising the scientific aims of the study.

**K.2. Screening (Pilot and General Studies):** At the screening session, the following procedures will take place:

1. The participant will receive a full, written explanation of study procedures and sign a consent form. Any questions will be answered, and a physician or nurse will be available to answer any medical questions.
2. Participants will be evaluated with a detailed medical and psychiatric history.
3. Complete physical examination (including vital signs, height, weight and abdominal circumference).
4. Laboratory tests, including standard screening blood tests (CBC with differential and platelet count, electrolytes, creatinine, BUN, liver enzymes, TSH), a urinalysis, urine toxicology use, urine pregnancy test (for premenopausal females), and electrocardiogram (EKG).
5. Participants will complete several questionnaires pertaining to personality.
6. IQ will be measured at screening using the Wechsler Test of Adult Reading or a comparable IQ measurement tool.

The screening process will take approximately 2 hours.

**K.3. Consenting (Pilot and General Studies):** Participants who meet entry criteria will be invited to meet with the research staff, who will fully explain risks and procedures as outlined in the consent form. After reviewing this information and answering questions, informed consent will be obtained from all participants. A copy of the consent form will be provided to all participants.

The consent process is a multistep process, whereby information about the risks and benefits of the study will be provided to potential participants across several sessions. The number of sessions over which this information will be provided will depend on how well the participant understands and retains the information. The process begins with the participant initiating contact via telephone. The research staff will provide a brief description of the study following which the participant is screened by a member of the research team. Thereafter, potentially eligible candidates are scheduled for a face-to-face interview. Participants will also be informed of all potential risks of participation. Participants will be required to read the informed consent form and the investigator will additionally describe the risks and discomforts.

To ensure that the study participant understands the study, the participant will be asked questions about the study procedures and the risks associated with participation. If any concern arises that the study participant did not fully understand the study, the PI may decide that the participant is not suitable for

participation. This process generally takes about one hour. If the participant is still interested after all questions have been answered, the PI or staff member consenting, will ask the participant to sign the informed consent form. Participants will be informed that they can decline to participate in the study without penalty and given the opportunity to withdraw from the study prior to analysis of their data. Following the resolution of any questions, the participants will be asked to sign the consent form if he/she agrees to participate.

Great care will be taken to ensure that the participant is able to give informed consent. If any concern arises that the study participant did not fully understand the study, the principal investigator may decide that the participant is not suitable for participation.

This process will involve careful explanation of the consent form by a member of the research staff. Non-research clinicians will be involved in the process when available.

**K.4. Justification of Cannabidiol Dose and Administration (Pilot and General Studies):** FDA-approved Cannabidiol, produced under Current Good Manufacturing Practice (cGMP), will be obtained from G.W. Pharmaceuticals, as "Epidiolex". The bioavailability of oral CBD is 13-19% and the elimination half-life is 56-61 hours . CBD is metabolized primarily in the liver, through the enzymes CYP3A4, UGTA7, UGTA and UGT2B7 isoforms . Importantly, CBD has a wide safety margin and was well-tolerated when co-administered with fentanyl, a high-potency opioid, in humans . The product will be stored in the VACHS research pharmacy as per package instructions. The research pharmacy will prepare CBD oil-based solutions and matching placebos, which will be administered by mouth by the study physician or nurse. CBD will be administered 24 hours after the last methadone/buprenorphine dose. A new IND is being pursued specifically for this project.

CBD is a non-rewarding compound with a wide safety margin . Further, CBD has been shown to produce central effects including hypnotic, anticonvulsive, anxiolytic and neuroprotective effects . CBD has been found to be a potent non-competitive inhibitor at CB-1 and CB-2 receptors  in addition to an allosteric modulator at kappa-opioid receptors, normalizing glutamatergic impairments induced by heroin self-administration . Moreover, CBD has been used in large clinical trials investigating its antipsychotic potential without significant adverse events .

The oral doses of CBD administered in this study will range from 400 mg to 1200 mg. Relatively low doses (400 mg) of oral CBD had anti-craving efficacy and were well-tolerated by people with OUD . Hence, 400 mg will be the lowest dose used in this proposal involving people with comorbid OUD and chronic pain. In preclinical studies, the doses of CBD required to inhibit pain were between 10 and 50 mg/kg . Even though CBD was safe and well tolerated in doses up to 4500 mg in adults (FDA Briefing Document, April 19, 2018, NDA 210365 Cannabidiol), the maximum recommended dose approved by the FDA is 20 mg/kg daily . The highest dose used in this study will be below maximum dose recommended by the FDA (up to 1200 mg in this study, compared to 1400 mg in a 70 kg or 155 lb person). Although higher doses can be used, this is a reasonable first step. Similarly, since CBD has never been administered to people comorbid OUD and chronic pain who are on opioid agonist maintenance, single doses in an open-label, dose-escalation paradigm will be used an initial safety procedure in pharmacotherapy development. The open-label, pilot safety phase will inform the doses used in the general study.

Although the half-life of CBD is up to 61 hours, its pharmacodynamic effects are short-lived, so that the interval of 72 hours between test sessions is not expected to generate carryover effects. First, Hurd and colleagues did not find carryover effects when administering 400 mg or 800 mg of CBD to recently abstinent persons with OUD, with intervals of 3-4 days between each test session . Notably, as in the current protocol, the first 2 of the 4 test sessions in this study were conducted following a single-dose of CBD . Second, the lack of carryover effects after a 72-hour interval is consistent with local experience conducting Phase 1 and Phase 2 human laboratory studies involving the administration of cannabinoids. For instance, Skosnik and colleagues studied individual and interactive effects of THC and CBD among healthy humans, with an interval of 72 hours between each test session . Third, other lines of evidence support the notion of a non-linear relationship between the clinical and pharmacokinetic effects of CBD –

such that the pharmacokinetics of CBD can vary widely, often without alteration in clinical effects. For instance, administering CBD with food may alter its pharmacokinetics, without significant change in its clinical effects: Among adults with epilepsy, in the fed state, the average Cmax of CBD was 14 times higher, and the AUC0 - ∞ was 4 times higher, compared to the unfed state; conversely, the antiseizure, neuropsychological, and safety profile of CBD remained unchanged in both conditions . Fourth, the relationship between the clinical – or pharmacodynamic – effects of drugs and their pharmacokinetic properties are often non-linear. This is especially true for highly lipid soluble drugs like cannabinoids, including THC and CBD. For example, although THC metabolites stay in the organism for several days or weeks – THC's elimination half-life ranges from 25 to 36 hours –, clinical effects like analgesia or sedation last only several hours.

As a result, cannabinoids like THC and CBD are often administered twice daily when used clinically, rather than once every 3 to 4 days, as if the pharmacokinetic and clinical effects were linear. We have an ongoing randomized, placebo-controlled, within-subject human laboratory study administering single doses of oral THC (10 mg or 20 mg) to persons with opioid use disorder treated with methadone, also has an interval of 72 hours between test sessions.

The latter study has been recently reviewed and approved by the VA HSS (MS0056) and the Yale IRB (Protocol # 2000027065; NCT04025359). Fifth, prior studies conducted at our center suggest that a longer interval is likely to increase attrition of the study population – persons with comorbid opioid use disorder and chronic pain –, such that data collection may be compromised. Finally, we are considering the pharmacokinetic effects of CBD on the main study outcomes, as exemplified by the repeated measurements of CBD and opioid levels in our protocol. Notably, both the FDA and NIDA are in accordance with the proposed interval of 72 hours.

For the general study Research Pharmacy will create a randomization sheet for this general study. Both the research team and participants will be blind to the randomization.

An Environmental Assessment is not required because the action requested qualifies for a categorical exclusion per 21 CFR 25.31(e). To the applicant's knowledge, no extraordinary circumstances exist per 21 CFR 25.15(d).

**K.5. Placebo (General Study):** The study interventions include CBD (open-label safety phase); and CBD or placebo (general study, following the safety phase). The container in which the study medication and placebo are dispensed will be labeled according to 21 CFR 312.6. "Caution: New Drug--Limited by Federal (or United States) law to investigational use." This study will recruit individuals receiving opioid agonist MAT. This study will not interfere with standard of care and will be in addition to treatment as usual. Safety assessments will be done in person during the scheduled experimental sessions. Furthermore, participants will be encouraged to remain compliant with their regular treatment sessions and medications.

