**Agitation Calmness Evaluation Scale (ACES):** The ACES consists of a single item that rates overall agitation and sedation at the time of evaluation, where 1 indicates marked agitation; 2, moderate agitation; 3, mild agitation; 4, normal behavior; 5, mild calmness; 6, moderate calmness; 7, marked calmness; 8, deep sleep; and 9, unarousable. The ACES is a well-validated instrument to assess sedation and has been used in various clinical trials.

**Field Test:** The field test will consist of a finger-to-nose test; a walk-and-turn test; a Romberg test. During the *finger-to-nose test*, participants will be asked to bring tip of the index finger up to touch the tip of the nose while his/her eyes are closed and his/her head is tilted slightly back, six times – three with each hand. During the *walk and turn test*, participants will be asked to take nine heel-to-toe steps along a straight line. After taking nine heel-to-toe steps, participants will then be directed to turn on one foot

and return in the same exact manner in the opposite direction. During the *Romberg test*, participants will be asked to stand with their feet together, head tilted back, and eyes closed for 30 seconds. The study physician will look for clues of changes from baseline, such as any loss of psychomotor coordination, loss of balance, eyelid/body tremors, muscle tone, and ability to follow directions.

**Positive and Negative Affect Schedule (PANAS)**: This is a 20-item, widely used measure of momentary mood states, has been found to be sensitive to the mood-altering effects of several substances .

Its reliability and validity have been extensively evaluated (Ref). The PANAS consists of 20 emotion words, with 10 loading on the Positive Affect factor and 10 on the Negative Affect factor (10). Sample words for Positive Affect include “alert”, “inspired”, and “enthusiastic”. Sample words for Negative Affect include “distressed”, “upset”, and “guilty”. Participants rate the degree to which they endorse each item on a rating scale (1 = very slightly or not at all; 5 = extremely). Items are then totaled to create a score for each factor: Positive Affect and Negative Affect. Higher scores represent greater endorsement of the construct. High levels of The PANAS will be used during each session and at each weekly outpatient session to measure the effects of CBD on mood.

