**Day 17:** Follow-up telephone contact.

Timepoint	Measures and Events
Baseline	VS, physical exam, ACES, MMSE, field test, Lab Assessments, EKG, SOWS, breathalyzer, urine drug testing, plasma opioid (methadone/buprenorphine) level, TLFB, SAFTEE, DEQ, CPT, HVLT, PANAS, AB, HCQ-14, PCS
0 min *	Cannabidiol (400, 800, 1200 mg) or placebo* administration
30 min	VS, SOWS, DEQ, PANAS
60 min	VS, DEQ, PANAS
90 min	VS, SOWS, cue session, AB, HCQ-14, pain measures plasma drug levels (blood)
120 min	VS, DEQ, PANAS, pain measures
150 min	VS, SOWS, DEQ, PANAS, pain measures
180 min	VS, DEQ, PANAS, CPT, HVLT
210 min	VS, SOWS, DEQ, PANAS, pain measures, methadone/buprenorphine administration
240 min to 420 min (buprenorphine) or 480 min (methadone)	VS, DEQ, PANAS, SAFTEE, HCQ-14, Plasma opioid and CBD levels, safety bloods and Lab Assessments (Day 10) Safety monitoring: VS, MMSE, ACES, field test hourly for at least 2 hours after the administration of methadone/buprenorphine → discharge if VS, MMSE, ACES are back to baseline
Follow-up	Safety follow-up by phone 8 hours after the administration of methadone/buprenorphine

\* The same schedule of events (Table 2) applies to the pilot study and the general study, except for time point 0 minutes. The difference is that in the pilot study, participants will receive 400 mg of CBD on the first test session,

800 mg in the second test session, and 1200 mg in the third test session, using dose-escalation and stopping criteria described in this protocol (Section K.1. subsection K.1.1). Conversely, the general study will have a randomized, placebo-controlled design, so participants will be assigned to CBD (400 mg, 800 mg, 1200 mg CBD) or placebo in a random order (Section K.1, subsection K.1.2.).

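### No observer sedation rating is planned between CBD/placebo and the opioid dose, although the sedation criterion counts ACES of 7 or more at any time in the session; the discharge clause also leaves out the field test

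*Combined protocol and SAP*

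**What the plan says.** Section K.1.1 (pilot) defines clinically significant sedation in two limbs. The first is "Agitation and Calmness Evaluation Scale (ACES) scores of 7 (marked calmness) or higher at any point during the session". The second is failure to return to baseline on vital signs, MMSE and field test "3 hours after the administration of buprenorphine, or 4 hours after the administration of methadone". Section K.6 describes the instrument as momentary: "The ACES consists of a single item that rates overall agitation and sedation at the time of evaluation".

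The timetable is Table 2 in section K.8, and its footnote gives its scope: "The same schedule of events (Table 2) applies to the pilot study and the general study". The only stated difference is what is given at 0 min. The baseline row lists ACES, MMSE and field test. The 180 min row reads "VS, DEQ, PANAS, CPT, HVLT", and the 210 min row reads "VS, SOWS, DEQ, PANAS, pain measures, methadone/buprenorphine administration". The row that opens at 240 min brings the three instruments back: "Safety monitoring: VS, MMSE, ACES, field test hourly for at least 2 hours after the administration of methadone/buprenorphine". The same row then allows "discharge if VS, MMSE, ACES are back to baseline".

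For the general study, section K.1.2 says that observation goes on if any sedation persists. Section M.1.3, which sits under a heading for both sub-studies, ends participation for significant sedation. It calls for consultation with the Data Safety Monitoring Board (DSMB) when its listed events occur in more than 3 participants.

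**The concern.** The first limb of the criterion covers the whole session, but the score it uses is not planned for the stretch in which CBD or placebo acts before the daily opioid is added. Because ACES rates only the moment, a rating after the opioid cannot recover the participant's state before it.

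At 210 min staff add a full daily dose of methadone or buprenorphine to as much as 1200 mg of CBD. Section L.1.1 lists somnolence among the common adverse reactions to CBD. At that step the physician has a baseline ACES from before CBD and none since. What is at stake is participant protection: an observer score at the point where the opioid is added, and consistent withdrawal for sedation.

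The discharge clause raises a smaller issue of the same kind. It names three measures and leaves out the field test, which K.1.1 treats as a recovery measure and which the same row schedules every hour.

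**Working it through.** The plan gives no figure to reproduce here. The check sets Table 2 beside K.1.1 row by row, followed by clock and session arithmetic.

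**Step 1. Rows after CBD/placebo (0 min) up to and including the opioid dose (210 min).**

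| Row (min) | Vital signs | DEQ (has a sedated item) | CPT/HVLT | ACES | MMSE | Field test |
|---|---|---|---|---|---|---|
| 30 | yes | yes | no | no | no | no |
| 60 | yes | yes | no | no | no | no |
| 90 | yes | no | no | no | no | no |
| 120 | yes | yes | no | no | no | no |
| 150 | yes | yes | no | no | no | no |
| 180 | yes | yes | yes | no | no | no |
| 210 | yes | yes | no | no | no | no |
| Total of 7 | 7 | 6 | 1 | 0 | 0 | 0 |

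**Step 2. First planned ACES after CBD/placebo.** The next row opens at 240 min, and 240 − 210 = 30 min after the opioid. If the hourly ratings start one hour after the opioid, the first comes at 210 + 60 = 270 min. So the first rating falls 30 to 60 min after the opioid in either sub-study.

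**Step 3. Share of the session without a planned ACES before the opioid.** Table 2 runs to 420 min (buprenorphine) or 480 min (methadone): 210/420 = 50% and 210/480 = 44%.

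**Step 4. The second limb of K.1.1.** Its check times are 210 + 180 = 390 min (buprenorphine) and 210 + 240 = 450 min (methadone). Both lie inside the windows that end at 420 and 480 min, so the schedule can serve this limb. The mismatch is confined to the first limb.

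**Step 5. Sessions concerned in the general study.** Completers: 34 × 4 = 136 sessions, of which 34 × 3 = 102 with CBD. If all 46 participants whom K.9 expects to enroll attended four sessions, the ceiling would be 46 × 4 = 184, of which 46 × 3 = 138 with CBD. These are planned sessions, not expected missed events.

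**Step 6. Discharge clause.** K.1.1 names three recovery measures: vital signs, MMSE and field test. The Table 2 clause names vital signs, MMSE and ACES. One of the three K.1.1 measures, the field test, is absent.

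**The case against.** The schedule may well be deliberate. The second limb of K.1.1 is timed from the opioid dose, and section L.1.1 discusses sedation when CBD is given with methadone or buprenorphine. Hourly ACES, MMSE and field test after the opioid therefore target the combined exposure. The first limb can also be read as a threshold for any rating taken, not as a rule on how often to rate. ACES is one item, and section M.5 has a physician and a team member present during all testing, so an unscheduled rating is always possible. Section L.1.1 also reports no evidence of sedation on ACES, MMSE and field test at all three doses in 4 methadone participants. All of this stands, and it keeps the point small. It does not put a planned observer score between CBD/placebo and the opioid, and the pilot result comes from 4 people.

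A reader might infer more than the documents support:

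- *That sedation goes unwatched for 210 min.* It does not. Vital signs with oximetry, self-rated sedation, CPT/HVLT and staff presence cover that stretch, and a baseline ACES precedes it.
- *That a rating at 210 min would show the effect of CBD alone.* Participants are at steady state on their opioid (K.1.1) and take CBD at trough opioid level (K.1.2). The rating would reflect CBD plus trough-level opioid.
- *That the general study has no workable sedation rule.* M.1.3 gives no definition and no pointer, but it also governs the pilot, where K.1.1 supplies the only definition in the protocol. A cross-reference would help; its absence is editorial.
- *That the DSMB would be left uninformed.* Section M.2 has safety data reviewed after every test day and by the investigator at least quarterly, and section M.3 gives the DSMB unblinded safety data. The trigger of more than 3 participants is not the only route.
- *That participants could be sent home impaired.* The field test is still done hourly, K.1.2 extends observation for lingering sedation, and M.1.3 and M.5 require a physician's assessment before discharge. Only the written condition is incomplete.

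**Conclusion.** The point holds as a minor mismatch between criterion and schedule. ACES, MMSE and field test are planned in 0 of the 7 rows from 30 to 210 min, and the first planned ACES after CBD/placebo comes 30 to 60 min after the opioid. The discharge clause omits one measure that its own row schedules.

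It does not weaken the primary safety comparison. Sections D.1 and K.10 rest that on SAFTEE, DEQ, CPT and HVLT, and ACES is not among them. No sample size, power or analysis figure changes.

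The conclusion assumes that Table 2 lists every planned rating. The cover letter reports pilot dosing in the past tense, so the benefit lies in the general study. How many of its 136 completer sessions remain is not stated, and the documents give no basis for estimating how many sedation episodes, if any, would be missed.

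**What to change.** 1. Table 2, 210 min row: add a single-item ACES before methadone or buprenorphine is given. The physician then has an observer score on CBD/placebo plus trough-level opioid before the full daily dose.
2. Table 2, discharge condition: add the field test to the measures that must have returned to baseline.

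Optional wording: in M.1.3, point significant sedation to the ACES limb of K.1.1 only. Pointing to the whole definition would turn slow recovery at 3 or 4 hours into a mandatory withdrawal, whereas K.1.2 answers it with continued observation. The second limb of K.1.1 needs no change.

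Cost: one one-item rating per session by staff already present, which is 1 × 4 = 4 per completer and 4 × 34 = 136 over 34 completers. Observation will occasionally last longer when the field test is still abnormal. If the optional pointer is adopted, an ACES of 7 or more would end participation for someone who might otherwise have continued. No extra visit, blood draw or analysis change is needed.
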